### **12.3 Medical Monitoring**

The sponsor will provide a medical monitor, a medical expert who advises the study investigators and monitors participant safety. The role of the medical monitor is to review all AEs/SAEs on a regular basis throughout the study, to advise the investigators on study-related medical questions or problems as needed, and to evaluate cumulative participant safety data and make recommendations regarding the safe continuation of the study.

### **12.4 Quality Assurance and Quality Control**

Each trial site shall be required to have Standard Operating Procedures (SOP's) to define and ensure quality assurance/control processes for trial conduct, data generation & collection, recording of data/documentation and reporting according to the protocol, GCP and any applicable local, national or international regulations.

## **13 DISCLOSURE AND PUBLICATION POLICY**

All information provided regarding the trial, as well as all information collected/documented during the course of the trial, will be regarded as confidential. The Sponsor reserves the right to release literature publications based on the results of the trial. Results from the trial will be published/presented as per the Sponsor's publication strategy.

Inclusion of the investigator in the authorship of any multi-center publication will be based upon substantial contribution to the design, analysis, interpretation of data, drafting and/or critically revising any manuscript(s) derived from the trial. The investigator acknowledges that the trial is part of a multi-center trial and agrees that any publication by the investigator of the results of the trial conducted at research site shall not be made before the first multi-center publication. In the event there is no multi-center publication within fifteen (15) months after the trial has been completed or terminated at all trial sites, and all data has been received, the investigator shall have the right to publish its results from the trial, subject to the notice requirements described herein and subject to acknowledgement of the Sponsor as appropriate. Investigator shall provide the Sponsor thirty days to review a manuscript or any poster presentation, abstract or other written or oral material which describes the results of the trial for the purpose only of determining if any

confidential or patentable information is disclosed thereby. If the Sponsor requests in writing, the investigator shall withhold any publication or presentation an additional sixty (60) days solely to permit the Sponsor to seek patent protection and to remove any site Confidential Information from all publications.

## 15 APPENDICES

### Appendix A: ECOG Performance Status Scale

ECOG Performance Status Scale	
Grade	Descriptions
0	Normal activity. Fully active, able to carry on all pre-disease performance without restriction.
1	Symptoms, but ambulatory. Restricted in physically strenuous activity, but ambulatory and able to carry out work of a light or sedentary nature (e.g., light housework, office work).
2	In bed < 50% of the time. Ambulatory and capable of all self-care, but unable to carry out any work activities. Up and about more than 50% of waking hours.
3	In bed > 50% of the time. Capable of only limited self-care, confined to bed or chair more than 50% of waking hours.
4	100% bedridden. Completely disabled. Cannot carry on any self-care. Totally confined to bed or chair.
5	Dead

## Appendix B: Contraceptive Guidelines and Pregnancy

### Women Not of Childbearing Potential are defined as Follows

Women are considered post-menopausal and not of child bearing potential if they have had 12 months of natural (spontaneous) amenorrhea with an appropriate clinical profile (e.g. age appropriate, history of vasomotor symptoms) or six months of spontaneous amenorrhea with serum FSH levels > 40 mIU/mL] or have had surgical bilateral oophorectomy (with or without hysterectomy) at least six weeks ago. In the case of oophorectomy alone, only when the reproductive status of the woman has been confirmed by follow up hormone level assessment is she considered not of child bearing potential.

### Contraceptive Guidelines for Women of Child-Bearing Potential

Women of child-bearing potential, defined as all women physiologically capable of becoming pregnant, must use highly effective contraception during the study and for 5 T1/2 plus an additional 4 weeks after stopping treatment. The highly effective contraception is defined as either:

1. True abstinence: When this is in line with the preferred and usual lifestyle of the subject. Periodic abstinence (e.g., calendar, ovulation, symptothermal, post-ovulation methods) and withdrawal are not acceptable methods of contraception.
2. Sterilization: have had surgical bilateral oophorectomy (with or without hysterectomy) or tubal ligation at least six weeks ago. In case of oophorectomy alone, only when the reproductive status of the woman has been confirmed by follow up hormone level assessment.
3. Male partner sterilization (with the appropriate post-vasectomy documentation of the absence of sperm in the ejaculate). For female subjects on the study, the vasectomised male partner should be the sole partner for that patient.
4. Use of a combination of any two of the following (a+b):
  - a. Placement of an intrauterine device (IUD) or intrauterine system (IUS).
  - b. Barrier methods of contraception: Condom or Occlusive cap (diaphragm or cervical/vault caps) with spermicidal foam/gel/film/cream/vaginal suppository.

The following are **unacceptable** forms of contraception for women of childbearing potential:

- Oral contraception, injected or implanted hormonal methods are not allowed as Tenalisib may potentially decrease the effectiveness of hormonal contraceptives.
- IUD progesterone T
- Female condom
- Natural family planning (rhythm method) or breastfeeding
- Fertility awareness
- Withdrawal
- Cervical shield

Women of child-bearing potential must have a negative serum or urine pregnancy test  $\leq 72$  hours prior to initiating treatment.

Fertile Males
Fertile males, defined as all males physiologically capable of conceiving offspring must use condom during treatment, plus additional 12 weeks after stopping treatment and should not father a child in this period.
Pregnancies

To ensure patient safety, each pregnancy in a patient on study treatment must be reported to Rhizen Pharmaceuticals SA within 24 hours of learning of its occurrence. The pregnancy should be followed up for 3 months after the termination of the pregnancy to determine outcome, including spontaneous or voluntary termination, details of the birth, and the presence or absence of any birth defects, congenital abnormalities, or maternal and/or newborn complications. Consent to report information regarding these pregnancy outcomes should be obtained from the mother.
 
Pregnancy is not considered a SAE. Initial and follow up information should be recorded on a Clinical Study Pregnancy Form and reported by the investigator to Rhizen Pharmaceuticals SA. Pregnancy follow-up should be recorded on the same form and should include an assessment of the possible relationship to the investigational drugs to any pregnancy outcome will also be captured on the pregnancy form. Any SAE experienced during pregnancy must be reported on the SAE Report Form.
 
Pregnancy outcomes must be collected for the female partners of any males who took study treatment in this study. Consent to report information regarding these pregnancy outcomes should be obtained from the mother.

**Appendix C: Response Criteria for iNHL- (Cheson et. al. 2014)**

Response and Site	PET-CT–Based Response	CT-Based Response
COMPLETE	Complete metabolic response	Complete radiologic response (all of the following)
Lymph nodes and extra lymphatic sites	Score 1, 2, or 3* with or without a residual mass on 5PS†	Target nodes/nodal masses must regress to ≤ 1.5 cm in LDi
	It is recognized that in Waldeyer's ring or extra-nodal sites with high physiologic uptake or with activation within spleen or marrow (e.g., with chemotherapy or myeloid colony-stimulating factors), uptake may be greater than normal mediastinum and/or liver. In this circumstance, complete metabolic response may be inferred if uptake at sites of initial involvement is no greater than surrounding normal tissue even if the tissue has high physiologic uptake	No extra lymphatic sites of disease
Nonmeasured lesion	Not applicable	Absent
Organ enlargement	Not applicable	Regress to normal
New lesions	None	None
Bone marrow	No evidence of FDG-avid disease in marrow	Normal by morphology; if indeterminate, IHC negative
PARTIAL	Partial metabolic response	Partial remission (all of the following)
Lymph nodes and extra lymphatic sites	Score 4 or 5† with reduced uptake compared with baseline and residual mass(es) of any size	≥ 50% decrease in SPD of up to 6 target measurable nodes and extra-nodal sites
	At interim, these findings suggest responding disease	When a lesion is too small to measure on CT, assign 5 mm × 5 mm as the default value
	At end of treatment, these findings indicate residual disease	When no longer visible, 0 × 0 mm For a node > 5 mm × 5 mm, but smaller than normal, use actual measurement for calculation
Nonmeasured lesions	Not applicable	Absent/normal, regressed, but no increase
Organ enlargement	Not applicable	Spleen must have regressed by > 50% in length beyond normal
New lesions	None	None
Bone marrow	Residual uptake higher than uptake in normal marrow but reduced compared with baseline (diffuse uptake compatible with reactive changes from chemotherapy allowed). If there are persistent focal changes in the marrow in the context of a nodal response, consideration should be given to further evaluation with MRI or biopsy or an interval scan	Not applicable

NO RESPONSE OR STABLE DISEASE	No metabolic response	Stable disease
Target nodes/nodal masses, extranodal lesions	Score 4 or 5 with no significant change in FDG uptake from baseline at interim or end of treatment	< 50% decrease from baseline in SPD of up to 6 dominant measurable nodes and extranodal sites; no criteria for progressive disease are met
Nonmeasured lesions	Not applicable	No increase consistent with progression
Organ enlargement	Not applicable	No increase consistent with progression
New lesions	None	None
Bone marrow	No change from baseline	Not applicable
PROGRESSIVE DISEASE	Progressive metabolic disease	Progressive disease requires at least 1 of the following
Individual target nodes/nodal masses	Score 4 or 5 with an increase in intensity of uptake from baseline and/or	PPD progression:
Extranodal lesions	New FDG-avid foci consistent with lymphoma at interim or end-of-treatment assessment	An individual node/lesion must be abnormal with: LDi > 1.5 cm and Increase by ≥ 50% from PPD nadir and An increase in LDi or SDi from nadir 0.5 cm for lesions ≤ 2 cm 1.0 cm for lesions > 2 cm In the setting of splenomegaly, the splenic length must increase by > 50% of the extent of its prior increase beyond baseline (eg, a 15-cm spleen must increase to > 16 cm). If no prior splenomegaly, must increase by at least 2 cm from baseline New or recurrent splenomegaly
Nonmeasured lesions	None	New or clear progression of pre-existing Nonmeasured lesions
New lesions	New FDG-avid foci consistent with lymphoma rather than another etiology (eg, infection, inflammation). If uncertain regarding etiology of new lesions, biopsy or interval scan may be considered	Regrowth of previously resolved lesions A new node > 1.5 cm in any axis A new extra nodal site > 1.0 cm in any axis; if < 1.0 cm in any axis, its presence must be unequivocal and must be attributable to lymphoma Assessable disease of any size unequivocally attributable to lymphoma
Bone marrow	New or recurrent FDG-avid foci	New or recurrent involvement

Abbreviations: 5PS, 5-point scale; CT, computed tomography; FDG, fluorodeoxyglucose; IHC, immunohistochemistry; LDi, longest transverse diameter of a lesion; MRI, magnetic resonance imaging; PET, positron emission tomography; PPD, cross product of the LDi and perpendicular diameter; SDi,

shortest axis perpendicular to the LDi; SPD, sum of the product of the perpendicular diameters for multiple lesions.

\* A score of 3 in many patients indicates a good prognosis with standard treatment, especially if at the time of an interim scan. However, in trials involving PET where de-escalation is investigated, it may be preferable to consider a score of 3 as inadequate responses (to avoid under treatment). Measured dominant lesions: Up to six of the largest dominant nodes, nodal masses, and extranodal lesions selected to be clearly measurable in two diameters. Nodes should preferably be from disparate regions of the body and should include, where applicable, mediastinal and retroperitoneal areas. Non-nodal lesions include those in solid organs (eg, liver, spleen, kidneys, and lungs), GI involvement, cutaneous lesions, or those noted on palpation. Non measured lesions: Any disease not selected as measured, dominant disease and truly assessable disease should be considered not measured. These sites include any nodes, nodal masses, and extranodal sites not selected as dominant or measurable or that do not meet the requirements for measurability but are still considered abnormal, as well as truly assessable disease, which is any site of suspected disease that would be difficult to follow quantitatively with measurement, including pleural effusions, ascites, bone lesions, leptomeningeal disease, abdominal masses, and other lesions that cannot be confirmed and followed by imaging. In Waldeyer's ring or in extranodal sites (eg, GI tract, liver, bone marrow), FDG uptake may be greater than in the mediastinum with complete metabolic response, but should be no higher than surrounding normal physiologic uptake (eg, with marrow activation as a result of chemotherapy or myeloid growth factors).

† PET 5PS: 1, no uptake above background; 2, uptake  $\leq$  mediastinum; 3, uptake  $>$  mediastinum but  $\leq$  liver; 4, uptake moderately  $>$  liver; 5, uptake markedly higher than liver and/or new lesions; X, new areas of uptake unlikely to be related to lymphoma.

11.	Protocol Deviations.....	19
12.	Listings.....	19
13.	References.....	20

List of Abbreviations

Abbreviation	Term
AE	Adverse Event
ATC	Anatomical Therapeutic Chemical
BID	Twice Daily
CI	Confidence Interval
CR	Complete Response
CT	Computed Tomography
CTCAE	Common Terminology Criteria for Adverse Events
DLT	Dose Limiting Toxicity
DoR	Duration of Response
DRC	Data Review Committee
ECG	Electrocardiogram
eCRF	Electronic Case Report Form
ECOG PS	Eastern Cooperative Oncology Group Performance Status
FAS	Full Analysis Set
FL	Follicular lymphoma
IgM	Immunoglobulin M
iNHL	Indolent non-Hodgkin's Lymphoma
IRB/IEC	Institutional Review Board/Independent Ethics Committee
LPL	Lymphoplasmacytic lymphoma
MedDRA	Medical Dictionary for Regulatory Activities
mITT	Modified Intent-to-Treat
MRI	Magnetic Resonance Imaging
MZL	Marginal Zone Lymphoma
NCI	National Cancer Institute
ND	Not Done
NE	Not Evaluable
NHL	Non-Hodgkin's Lymphoma
ORR	Objective Response Rate
PET	Positron Emission Tomography
PFS	Progression-Free Survival
PP	Per-Protocol
PR	Partial Response
PT	Preferred Term
Q1	First Quartile
Q3	Third Quartile
QTcF	QT interval with Fridericia's correction
SAE	Serious Adverse Events
SAP	Statistical Analysis Plan
SAS	Statistical Analysis Software
SD	Stable Disease
SOC	System Organ Class
SLL	Small Lymphocytic Lymphoma
TEAE	Treatment-Emergent Adverse Event
TID	Thrice Daily
WHO	World Health Organization
WM	Waldenstrom Macroglobulinemia

1. Amendments from Previous Version(s)

Not Applicable.

2. Introduction

Note: In this document, any text taken directly from the protocol (Number RP6530-1802, Amendment 1 to Version 1.0, Dated 15 March 2018; Amendment Version dated 04 December 2018) is *italicized*.

This SAP provides the detailed methodology for summary and statistical analyses of the data collected in study RP6530-1802. This document may modify the plans outlined in the final protocol.

2.1 Rationale

Approximately one third of NHLs are indolent. These indolent NHLs (iNHLs) are slow-growing tumors with a prolonged natural history, and most patients present with advanced disease. iNHLs are highly treatable but rarely cured.

The safety and tolerability of Tenzalisib has been established up to doses of 1200 mg BID and 800 mg TID. In recent study, Tenzalisib 800 mg BID (Fasting) is established as a MTD dose in patients with T-cell lymphoma. Therefore, Tenzalisib (800 mg BID) is considered for this study. It is expected that proposed monotherapy has the potential to improve response rates in the proposed patient population.

3. Study Objectives

3.1 Primary Objective

- *To assess the anti-tumor activity of Tenzalisib, as determined by the Objective Response Rate (ORR), Duration of Response (DoR) and Progression Free Survival (PFS).*

3.2 Secondary Objective

- *To characterize safety and tolerability of Tenzalisib in patients with iNHL.*

4. Study Endpoints

4.1 Efficacy Endpoints

- *ORR is defined as sum of CR and PR rates and will be assessed according to the Lugano Classification for initial evaluation, staging, and response assessment of Non-Hodgkin lymphoma. (Cheson-2014)*
- *CR rate will be assessed according to the Lugano Classification for initial evaluation, staging, and response assessment of non-Hodgkin lymphoma.*
- *DoR is measured from the initial response to disease progression or death.*

- *PFS is defined as the time of the first dose of Tenalisib to disease progression or death.*

4.2 Safety Endpoints

- *Adverse Event (AE), Grade 3/4 AEs, Serious and fatal Adverse Event (SAE), graded using NCI CTCAE Version 5.0.*

5. Study Design

The study is designed as a Phase II, open label, two parts study in relapsed/refractory iNHL patients. The mandatory Part 1 of the study will assess the efficacy and safety of Tenalisib in 20 patients with iNHL. After all patients enrolled in Part 1 have had the opportunity to provide at least three tumor outcome assessments, the Data Review Committee (DRC) will evaluate the efficacy (anti-tumor activity) and safety results for each of the subtypes (e.g. FL, MZL or WM). If the committee believes there are potential clinically meaningful responses for certain subtype, the committee will recommend initiation of Part 2 to evaluate efficacy and safety for that subtype. If not, the study will be terminated without initiating Part 2. The sample size for Part 2 will be derived based on the outcome from Part 1. Data from Part 1 will not be included in the analysis of Part 2 of the study.

The study treatment Tenalisib (800 mg BID) will be administered orally in 28-days of cycle over a period of 8 months in absence of definitive disease progression or unacceptable toxicity. Treatment will be continued in patients experiencing clinical benefit until the occurrence of definitive disease progression, unacceptable toxicity, or withdrawal from the study due to investigator decision or other reasons; maximum for up to 24 months.

The efficacy response will be evaluated on Weeks 8 (C3D1± 7 days), Weeks 16 (C5D1± 7 days) and then every 12 weeks thereafter, and/ or at the EOT or as clinically indicated (if clinical progression is suspected or for confirmation of complete response/disease progression).

Group	N	Patient population	Tenalisib
Part 1	20	Refractory/ relapsed iNHL.	800 mg BID in 28-Days Cycle for 8 Cycles¹
Part 2	The sample size will be derived based on the outcome from Part 1	Refractory/ relapsed iNHL patients of one of the specific subtype (e.g. FL, MZL, WM)	800 mg BID in 28-Days Cycle for 8 Cycles¹

¹*Post cycle 8, treatment will be continued in patients experiencing clinical benefit up to 24 months unless progression of disease or toxicity warranting discontinuation of therapy. The decision to continue the treatment will be determined by the PI after consultation with Sponsor on case to case basis.*

5.1 *The Expected Duration of Subject Participation and Follow-up*

The expected duration of subject participation in the study will be 8 months. Treatment will be continued in patients experiencing clinical benefit up to 2 years unless progression of disease or toxicity warranting discontinuation of therapy. The decision to continue the treatment will be taken by PI after consultation with sponsor on case to case basis.

Notes:

- After reviewing the emerging efficacy data, the study has been closed due to absence of clinically meaningful response to single agent Tenalisib in Part 1 of the study. Therefore, Part 2 will not be performed.
- The analysis proposed in this SAP is considering the available data at the time of completion of the study.
- The data on DLT was erroneously captured on the CRF and which is not applicable for this study. Hence, the DLT information will not be displayed in any of the reports.

6. **Sample Size Considerations**

The sample size for Part 1 is not based on statistical considerations. After all patients enrolled in Part 1 had the opportunity to provide at least three tumor outcome assessments, the DRC will evaluate the efficacy and safety results for each of the subtypes. If the committee believes there are potential clinically meaningful benefits for certain subtype, the committee will recommend initiation of Part 2 to evaluate efficacy and safety for that subtype. The sample size for Part 2 will be derived based on ORR data from Part 1.

***Part 1:** 20 patients with relapsed/refractory iNHL will be enrolled.*

Part 2 will not be initiated as the study is closed due to absence of clinically meaningful response to single agent Tenalisib

7. **Analysis Populations**

The following 4 analysis populations are planned for Part 1 of the study.

7.1 **Modified Intent-to-Treat Population (mITT)**

The mITT is the primary efficacy analysis population and will include data from all patients who received at least 1 dose of study medication and provide at least 1 post-baseline efficacy assessment.

7.2 **Per-Protocol (PP) Population**

The PP Population is a subset of the modified Intent-to-Treat Population and will include patients without major protocol deviations.

Major deviations shall include:

-
- Deviation from an IEC/IRB approved protocol which compromise the safety and welfare of participating subjects or the integrity of the study and /or the completeness, accuracy and reliability of study data. Examples deviations included but not limited to:
 - o Failure to obtain informed consent (e.g., there is no documentation of informed consent) for a subject;
 - o Informed consent is obtained after initiation of study procedures;
 - o Enrollment of subject who has failed to meet the inclusion/exclusion criteria.

The list of protocol deviations with categorization with respect to major and minor deviations will be generated. This population will also be used for efficacy assessment.

Note: In situation, the patients qualifying for mITT set are same as the patients qualifying for PP set, the respective tables and figures proposed using PP set will not be produced to avoid the duplication of the results.

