## **9.3 Study Population**

The following 3 analysis populations are planned for Part 1 of the study. Analysis population for Part 2 will be redefined based on the results of Part 1.

- Modified Intent-to-Treat Population (mITT): the mITT is the primary efficacy analysis population and will include data from all patients who received at least 1 dose of study medication and provide at least 1 post-baseline efficacy assessment.
- Per-Protocol (PP) Population: the PP Population is a subset of the modified Intent-to-Treat Population and will include patients without major protocol deviations.
- Safety Population: the Safety Population will include all subjects who receive at least 1 dose of the study drug.

Membership in the analysis populations will be determined before database lock.

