10.5 Efficacy Analysis

Analysis Set: mITT and PP

- The analysis will be done as per the disease subtypes [Follicular lymphoma (FL), Marginal zone lymphoma (MZL), Waldenstrom's macroglobulinemia (WM) and Small lymphocytic lymphoma (SLL)] and overall.

Note: The analyses outlined below are subject to availability of adequate data. In absence of adequate data, some of the efficacy endpoints discussed below will be presented with basic summaries and/or plots and listings, as appropriate.

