10.5.1 Objective Response Rate (ORR)

It is defined as sum of CR and PR rates. Only those patients who have had a pre-treatment baseline efficacy evaluation and at least one post-treatment efficacy evaluation or confirmed disease progression will be considered evaluable for response. [Subtype specific](#) and overall ORR will be calculated.

Additionally, Disease Control Rate (DCR= CR+PR+SD) will be presented.

This data will be summarized using frequency, and percentage. Due to low number of patients observed in each of the disease subtype, the 95% CI (Using exact method based on binomial distribution, subject to availability of adequate data) will be presented for the Overall group only.

The corresponding listing will also be provided.

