10.5.3 Progression Free Survival (PFS)

It is defined as time of the first dose of Tenalisib to disease progression or death. Subjects who die without a reported prior progression will be considered to have progressed on the date of their death. Subjects who did not progress or die will be censored on the date of their last tumor assessment.

This data will be summarized using the Kaplan-Meier method and displayed graphically per the [disease subtype](#) and Overall. The following reports will be generated:

- The Q1, median and Q3 PFS time will be provided. Due to low number of patients observed in each of the disease subtype, 95% CI for the Q1, median, and Q3 PFS time will be presented for the Overall group only using Brookmeyer-Crowley method subject to availability of adequate data.
- The number and % of patients with disease progressive events (further divided into progression or death) will be provided.
- The number and % of patients censored (further divided by reasons for censoring) will be provided.
- Kaplan-Meier curves will be produced.
- A listing of PFS data will be provided.

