10.5.5 Best Overall Response

It is the best response recorded from the start of the treatment until disease progression or discontinuation from the study.

This data will be summarized using frequency and percentage for Complete Response (CR), Partial Response (PR), Stable Disease (SD), and Progressive Disease (PD), as captured in the CRFs, per the [disease subtype](#) and overall. This data will also be listed.

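### Treated patients with no post-baseline assessment fall out of every efficacy analysis, so a death before the first assessment is never counted as a PFS event

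*SAP*

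**What the plan says.** - **Efficacy sets.** Protocol 9.3 states that "the mITT is the primary efficacy analysis population". SAP 7.1 repeats the rule: the set holds patients "who received at least 1 dose of study medication and provide at least 1 post-baseline efficacy assessment". The PP set (SAP 7.2) is mITT without major deviators.
- **Where efficacy is analysed.** SAP 10.5 opens with "Analysis Set: mITT and PP", which covers ORR, CR rate, PFS, DoR and best overall response.
- **PFS event.** SAP 10.5.3 measures from first dose and adds: "Subjects who die without a reported prior progression will be considered to have progressed on the date of their death". It sets no condition that an assessment came first. It also promises an event table: "The number and % of patients with disease progressive events (further divided into progression or death) will be provided".
- **Evaluability for response.** SAP 10.5.1 and 10.5.2 require a baseline evaluation and "at least one post-treatment efficacy evaluation or confirmed disease progression will be considered evaluable for response". The progression alternative is not in SAP 7.1, and death is not named.
- **Best overall response.** SAP 10.5.5 has rows for CR, PR, SD and PD. The abbreviation list defines NE as "Not Evaluable", but no planned summary uses it.
- **All-treated set.** The Safety Population (SAP 7.3) holds everyone dosed but serves safety outputs only. The FAS (SAP 7.4) serves baseline, history, medication and deviation outputs.

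**The concern.** The PFS definition and the population it is applied to do not fit together. The definition counts a death at any time from first dose. The population admits a patient only after an efficacy assessment, first scheduled at week 8. A treated patient who dies unassessed is a PFS event by definition and absent by construction. Treated patients with no assessment for other reasons also leave the ORR, CR and disease control denominators.

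The trial has no control arm, and SAP 9.1 states no formal hypotheses, so the estimates are the result. Where leaving these patients out changes an estimate, it does so in the drug's favour: PFS events are lost and response denominators shrink. At stake is the accuracy of the reported ORR and PFS, not a test or a decision.

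**Working it through.** The plan gives no figure to reproduce: the 20 patients of Part 1 have no statistical basis (SAP 6). The check is a trace through the sets, then an illustration of size.

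**1. Trace.** A patient is dosed and dies before any assessment.
- mITT: out, because there is no post-baseline assessment.
- PP: out, because it is a subset of mITT.
- Safety and FAS: in, but neither is assigned an efficacy analysis.
- PFS event count and curve: the death is absent.

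The only opening is the sentence in Protocol 9.4.3 that allows additional analyses. It permits them but plans none.

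**2. Who is affected.** Protocol Table 1 marks imaging and response assessment at EOT, Protocol 6.7 and 6.9 refer to that table, and unscheduled assessments are done when clinically indicated. Most early leavers are therefore assessed. The gap is confined to patients who die, withdraw consent or miss EOT with no assessment of any kind. Deaths after a first assessment are counted as SAP 10.5.3 intends.

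**3. Response.** Inputs, all assumed: 20 treated (planned enrolment; the number treated is not given), r responders, u unassessed. ORR is r/20 in all treated and r/(20 − u) in mITT. Exact 95% limits are the Clopper-Pearson ones: with n the denominator, the lower is the 2.5% point of Beta(r, n − r + 1) and the upper the 97.5% point of Beta(r + 1, n − r).

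| r | All treated, n = 20 | u = 1, n = 19 | u = 2, n = 18 |
|---|---|---|---|
| 4 | 20.0% (5.7–43.7) | 21.1% (6.1–45.6) | 22.2% (6.4–47.6) |
| 1 | 5.0% (0.1–24.9) | 5.3% (0.1–26.0) | 5.6% (0.1–27.3) |
| 0 | 0%, upper 16.8% | 0%, upper 17.6% | 0%, upper 18.5% |

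The largest shift is 22.2 − 20.0 = 2.2 points, against intervals about 17 to 41 points wide.

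**4. PFS.** Let d patients die before any assessment, with no earlier censoring or other early event. Just before week 8 the all-treated curve stands at (20 − d)/20: 95% for d = 1 and 90% for d = 2. The mITT curve stands at 100% in both cases.

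Quartiles follow the SAS rule (the midpoint of adjacent event times when the curve equals the target exactly) and assume distinct times. Progressions are numbered among the 20 − d assessed patients.

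| d | Q1, mITT | Q1, all treated | Median, mITT | Median, all treated |
|---|---|---|---|---|
| 1 | 5th | midpoint of 4th and 5th | 10th | midpoint of 9th and 10th |
| 2 | 5th | midpoint of 3rd and 4th | midpoint of 9th and 10th | midpoint of 8th and 9th |

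**5. Three tied patterns.**
- d = 2, with 3 progressions at week 8 and 3 at week 16. mITT: 15/18 = 0.833, then 12/18 = 0.667, so Q1 = 16 weeks. All treated: 15/20 = 0.75 exactly at week 8, so Q1 = (8 + 16)/2 = 12 weeks.
- d = 1, same progressions. mITT: 16/19 = 0.842, then 13/19 = 0.684. All treated: 16/20 = 0.80, then 13/20 = 0.65. Q1 = 16 weeks in both.
- d = 2, with 2 progressions at week 8 and 4 at week 16. mITT: 16/18 = 0.889, then 12/18 = 0.667. All treated: 16/20 = 0.80, then 12/20 = 0.60. Q1 = 16 weeks in both.

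The curve and event count always change when d is above 0; a reported quartile may or may not.

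**The case against.** The strongest reply is that the group is probably tiny and its members would be visible. Eligibility requires a life expectancy of at least 3 months, beyond the week-8 scan, and the disease is described as slow-growing. SAP 10.1 tabulates discontinuation reasons and set sizes for all patients, SAP 10.6.2 plans a deaths summary, and SAP 12 lists withdrawals and analysis populations. SAP 10 also provides a Missing row in count tables where needed. With the study closed, an added analysis would be post hoc.

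Much of this stands. The group may be empty, and a reader could work out all-treated ORR and CR from the set sizes. But the Missing row does not bring anyone into mITT, and no listing puts a death into the PFS curve, event count or quartiles. Visibility is not assured either: Protocol 7.4.4 sends deaths attributed solely to progression to the Trial Discontinuation form and keeps them out of SAE reporting.

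A second reply is that the progression alternative in SAP 10.5.1 could already make some early progressors evaluable. That is fair, and it means that aligning SAP 7.1 with it could change who is in mITT. It still does not cover a death without confirmed progression.

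It is also right that treating unassessed patients as non-responders is a conservative convention rather than known truth, and that with no responders the ORR estimate itself does not move.

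**Conclusion.** The concern holds, as a minor point. Followed as written, the plan excludes from both efficacy sets a death that its own PFS definition counts, and no planned efficacy output restores it. With 20 treated patients assumed, each such death costs one event and 5 points on the early all-treated curve. With one or two unassessed patients and the response counts tried, ORR moves by 0 to 2.2 points. The numbers of treated, unassessed and early-death patients are assumptions, because the documents give none of them; if no treated patient went unassessed, the effect is zero. The closure for lack of response and the decision not to run Part 2 are unaffected.

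**What to change.** Keep mITT as the primary set. In SAP 7 and 10.5, add a supplementary analysis, labelled as such, of PFS, ORR, CR rate, disease control rate and best overall response in the Safety Population of SAP 7.3:

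- use all treated patients as the denominator, overriding the non-missing default in SAP 10;
- show unassessed patients in an NE row and count them as non-responders;
- count deaths before the first assessment as PFS events on the date of death;
- censor living patients with no post-baseline scan at day 1. The current rule censors at the last tumour assessment, which for them would be the baseline scan taken before first dose.

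If the Safety Population and mITT turn out identical, state so and omit the duplicate output, as SAP 7.2 already does for PP. Separately, reconcile SAP 7.1 with the confirmed-progression alternative in SAP 10.5.1 and 10.5.2, and note any change in mITT membership that results.

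The cost is one column per efficacy table and one PFS curve, or one sentence if the sets coincide. The drawback is that the analysis is chosen after the efficacy conclusion is known, so it must be documented as an addition to Protocol 9.3.
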